### Sham Intervention Description

Subjects randomized to the Sham System will receive a research phone and research watch (as did those randomized to the Active System) and a version of the NW Application that has the threshold set extremely high (so high that it will NEVER be activated) will be installed. The Sham System will have the same user interface on the smartwatch (start button is enabled and is indistinguishable from the user interface present in active mode). The Sham System (as well as the Active System) will vibrate whenever the subject hits the "START" button. The Sham System will monitor the wearer's sleep pattern, as the active system does but will not provide any interventions during the night.

## 3. OBJECTIVES AND OUTCOMES

OBJECTIVES	OUTCOMES	JUSTIFICATION FOR OUTCOMES
Primary Efficacy		
To demonstrate that the NW digital therapeutic improves sleep quality in subjects with PTSD	Difference between average PSQI score at baseline (Day 0) and average PSQI score at post-treatment (Day 30) assessment	The NW digital therapeutic is expected to improve sleep quality. PSQI is a validated measure of subject-reported sleep quality
Primary Safety		
To assess the potential risk of worsening sleep quality	Difference between average Epworth Sleepiness Scale (ESS) at baseline (Day 0) and ESS at Day 30.	The Epworth Sleepiness Scale is a validated measure of daytime somnolence.

To assess the potential worsening of suicidal risk	Difference between the average Columbia-Suicide Severity Rating Scale (C-SSRS) at baseline (Day 0-Lifetime and Recent version) and C-SSRS at Day 30 (Since Previous Contact version)	The Columbia-Suicide Severity Rating Scale is a validated measure of suicide risk.
Secondary: Observational		
To evaluate changes in subjective sleep quality.	Difference in PSQI-A and NW Likert Scale for Sleep Quality between baseline (Day 0) and post-treatment (Day 30) in the Active System.	May show improved sleep quality on scales other than PSQI.
To evaluate changes in PTSD and/or depression symptoms.	Difference in PCL-5 and PHQ-9 between baseline (Day 0) and post-treatment (Day 30) in the Active System.	The NightWare digital therapeutic may improve PTSD and/or depression symptoms. Therefore, this is an observational endpoint.
To evaluate changes in quality of life	Difference in FOSQ-10 and VR-12 between baseline (Day 0) and post-treatment (Day 30) in the Active System.	Improved sleep quality may improve quality of life
To evaluate changes in nightmare severity and frequency	Difference in TRNS between baseline (Day 0) and post-treatment (Day 30) in the Active System.	The TRNS is a validated measure of nightmare frequency and severity.
To evaluate changes in insomnia symptoms	Difference in ISI between baseline (Day 0) and post-treatment (Day 30) in the Active System	Decreased sleep latency and reduced sleep disturbance were noted as major areas of improvement in sleep quality on interim and secondary analyses of current data. Treatment of nightmares may improve insomnia symptoms.

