Objectives:	
Primary Objectives:
 
 
● Demonstrate that the Active System improves sleep quality as assessed by the Pittsburgh Sleep Quality Index (PSQI) in participants with PTSD
 
● Demonstrate that improvement in sleep quality is greater for the Active System than the Sham System
 
● Demonstrate that the Active System does not lead to worsening of daytime sleepiness as assessed by the Epworth Sleepiness Scale (ESS)
 
● Demonstrate that there is not an increase in suicide risk as assessed by the Columbia-Suicide Severity Rating Scale (C-SSRS)
 
 
Secondary Objectives:
 
 
● Evaluate changes in the following measures between Day 0 (baseline) and Day 30: 
 
- PTSD severity [PTSD Checklist (PCL-5)]
 
- Sleep quality [PSQI Addendum for PTSD (PSQI-A)]
 
- Subjective sleep quality [NW Likert Scale for Sleep Quality]
 
- Quality of life [Functional Outcomes of Sleep Questionnaire (FOSQ-10) and Veterans Rand 12 Quality of Life instrument (VR-12)]
 
- Nightmare severity/frequency [TRNS]
 
- Depression symptoms [Patient Health Questionnaire-9 (PHQ-9)]
 
 
 

	- Insomnia Severity Index (ISI)
Outcomes:	
Primary Efficacy Outcomes:
 
 
● Difference between PSQI score at baseline (Day 0) and average PSQI score at the post-treatment assessment (Day 30) [i.e., PSQI change] in the Active System.
 
● Difference in average PSQI change scores between Active System and Sham System conditions.
 
 
Primary Safety Outcomes:
 
 
● No significant increase in ESS between baseline (Day 0) and Day 30 in the Active System.
 
● No increase in C-SSRS severity score between Day 0 and Day 30 in the Active System.
 
 
Observational Outcomes:
 
 
● Improvement in sleep quality, nightmare frequency/intensity, quality of life, PTSD severity, and depression symptoms between Day 0 and Day 30 in the Active System.
 
● Greater improvement in sleep quality, nightmare frequency/intensity, quality of life, PTSD severity, and depression symptoms in the Active System relative to the Sham System.
 

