### 5.1. Inclusion Criteria

#### Inclusion Criteria

- Either Diagnosis of PTSD via American Psychiatric Association PTSD diagnostic criteria in the fifth edition of its Diagnostic and Statistical Manual of Mental Disorders (DSM-5) or having symptoms consistent with PTSD (subject must score at least 25 on the PTSD Checklist-5 to qualify for the study).
- Equal to or older than 22 years of age.
- Proficient in both reading and writing in the English language.
- Pittsburgh Sleep Quality Index (PSQI). Potential participants would need to score 10 or more to qualify.
- ESS: On question #8 any score above “0” will prompt an additional question:
  - Do you drive (“get behind the wheel”) when you are drowsy?
    - Answer must be “No” to be enrolled in the study due to safety concerns.
- Have repetitive nightmares contributing to disrupted sleep as reported by the subject
- Wireless Internet and two power outlets where they sleep
- Prazosin use; if yes, subject may be included if willing to be tapered by prescribing provider.
  - Taper must be completed, and the subject must be off prazosin for 2 weeks prior to enrollment.
- Alpha blocker use; if yes, subject may be included if willing to be tapered by prescribing provider. Taper must be completed, and the subject must be off all alpha blockers for 2 weeks prior to enrollment.

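### The Synopsis makes an Active-only PSQI change a primary efficacy outcome and Section 3 leaves out the sham comparison, in conflict with the sham-controlled tests in Sections 7.2, 7.3 and 7.6 and the SAP

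*Protocol*

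**What the plan says.** Protocol Section 1.1 (Synopsis) sets two primary efficacy objectives, each with its own outcome. The first objective reads "Demonstrate that the Active System improves sleep quality as assessed by the Pittsburgh Sleep Quality Index (PSQI) in participants with PTSD", and its outcome is the Day 0 to Day 30 change in PSQI in the Active arm. The second outcome is "Difference in average PSQI change scores between Active System and Sham System conditions". Nothing says whether both must be met or in what order they are tested.

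Section 3 has a single primary efficacy row: "Difference between average PSQI score at baseline (Day 0) and average PSQI score at post-treatment (Day 30) assessment". It mentions neither an arm nor sham. The five secondary rows are all within-arm: "Difference in PSQI-A and NW Likert Scale for Sleep Quality between baseline (Day 0) and post-treatment (Day 30) in the Active System"; "Difference in PCL-5 and PHQ-9 between baseline (Day 0) and post-treatment (Day 30) in the Active System"; "Difference in FOSQ-10 and VR-12 between baseline (Day 0) and post-treatment (Day 30) in the Active System"; and the TRNS and ISI rows in the same form.

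The analysis sections are built differently. Section 7.2 states the primary hypothesis against sham, tests it with a two-sample t-test, and claims a one-sided type I error of 2.5%. Section 7.3 powers that contrast. Section 7.6 and the SAP plan two-sample t-tests of the secondary hypotheses. The Synopsis also lists, among its observational outcomes, greater improvement on Active than on Sham for sleep quality, nightmares, quality of life, PTSD severity and depression. Insomnia is not named in that list.

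**The concern.** The outcome definitions and the tests do not match. Someone working from Section 3 would define the trial's efficacy outcomes without the control arm. Someone working from Section 7.2 would define the primary one as a difference between arms. Someone working from Section 1.1 would find both and no rule for a split result.

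The difference matters because a before-after change in one arm keeps everything the sham arm is there to remove. Participants must have a raised PSQI to enter ("Potential participants would need to score 10 or more to qualify"). Section 6.4 scores the PSQI and settles eligibility at the Day 0 visit, and that same score is the baseline, so some regression to the mean is expected. Participants also receive a device, training, calls and daily questions, and they report their own sleep. Scores can fall for these reasons with a device that does nothing.

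At stake is which result counts as showing efficacy. If the Active arm improved and the sham comparison failed, Section 1.1 would still allow one of its primary objectives to be reported as met.

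**Working it through.** **1. The plan's own figure.** Inputs from Section 7.3: difference 3 points, SD 5 in each arm, 90% power, 60 completers per arm. From Section 7.2: two-sided 0.05 with the direction favouring Active, so 2.5% one-sided.

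- Normal approximation: n per arm = 2 × (1.960 + 1.282)² × 5² / 3² = 58.4, rounded up to 59.
- Two-sample t-test with 60 per arm: noncentrality 3 / (5 × √(2/60)) = 3.29, power 90.3%.
- With three O'Brien-Fleming looks (Section 7.4), by simulation: 90.4%.
- Enrolment: 120 / (1 − 0.5) = 240.

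The figure reproduces. It belongs to Active versus Sham. The plan gives no power or rejection rule for an Active-only efficacy outcome.

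**2. What an Active-only test would do with no device effect.** Suppose both arms fall by the same non-specific amount c. The documents give no value for c, so it is an assumption shown over a range. For a one-sample t-test of the Active-arm change at one-sided 2.5%, the noncentrality is c / (5/√n). At n = 60 this is c / 0.645, that is 1.55, 3.10 and 4.65 for c = 1, 2 and 3. For Active versus Sham the expected difference is c − c = 0, whatever c is.

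| Assumed shared fall c (points) | Active-only test, n = 60 | Active-only test, n = 120 | Active versus Sham |
|---|---|---|---|
| 0 | 2.5% | 2.5% | 2.5% |
| 0.5 | 11.5% | 19% | 2.5% |
| 1 | 33% | 58% | 2.5% |
| 1.5 | 63% | 90% | 2.5% |
| 2 | 86% | 99% | 2.5% |
| 3 | 99.5% | about 100% | 2.5% |

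The n = 60 column is the planned minimum number of completers per arm; n = 120 means no attrition. A smaller SD makes the problem worse: at n = 60 and c = 1 the probability is 33% for SD 5, 48% for SD 4 and 72% for SD 3 (SDs of 4 and 3 are assumptions).

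**3. How much of c could be regression to the mean.** For a normal score with mean μ, SD s and retest correlation r, selected at 10 or more (cut at 9.5 for whole-number scores), the expected fall is (1 − r) × s × φ(a) / (1 − Φ(a)), with a = (9.5 − μ)/s. The documents give none of μ, s or r for the unselected population. Over assumed ranges of μ 10 to 14, s 3 to 5 and r 0.7 to 0.9, the fall runs from 0.04 (μ = 14, s = 3, r = 0.9) to 1.1 points (μ = 10, s = 5, r = 0.7). A fall of 2 or 3 points would therefore need a placebo or time effect as well.

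**The case against.** The strongest reply is that the confirmatory efficacy analysis is already sham-controlled. Section 7.2 has one primary hypothesis, against sham, with its own test and rejection rule, and Section 7.3 powers it. No section sets out a one-sample efficacy test. This stands, and it means the 33%, 86% and 99.5% describe a test a reader might infer from Section 1.1, not one that Section 7.2 prescribes. That route is not clearly closed, however. Section 7.5 and the SAP say that the one-sample safety tests are done in a similar way to the primary efficacy hypothesis. Section 7.2 also leaves a repeated-measures test of PSQI change to the statistician's judgement. The SAP as supplied has no primary efficacy section that would settle the matter.

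The two primary outcomes can also be read jointly, since the Synopsis hypothesis joins improvement on Active with greater improvement than on Sham. A both-must-pass rule would hold the false-positive rate at or below 2.5%. No section states that rule.

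The Section 3 PSQI row names no arm, so it could mean the participant-level change that Section 7.2 then compares between arms. That reading is fair for this row. It does not rescue the secondary rows, which name the Active arm.

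A reader might infer that the trial has no controlled efficacy comparison, or that claims on PTSD, depression and quality of life would rest only on the Active arm. The documents do not support this. The Synopsis lists Active-versus-Sham outcomes for these domains, Section 7.6 and the SAP plan two-sample tests, and Section 3 labels the rows observational. Nor does selection push every scale the same way. PHQ-9 scores of 20 or more are excluded, which favours a later rise, and it is unclear whether the PCL-5 threshold applies to participants with a formal diagnosis.

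**Conclusion.** The point holds as a conflict over what the efficacy outcomes are. Section 1.1 calls an uncontrolled change primary without saying how it combines with the controlled one, and Section 3 omits sham from its primary efficacy row and all five secondary rows. Sections 7.2, 7.3 and 7.6 and the SAP compare Active with Sham. The Active-only outcome, taken alone, cannot support a claim that the device improves sleep quality.

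The size is conditional. The probabilities in the table assume a one-sample t-test that Section 7.2 does not specify, the plan's SD of 5, no device effect, and an assumed non-specific fall. Regression to the mean alone probably accounts for about a point at most under the ranges tried. The sham-controlled test is unaffected, and its 90% power reproduces.

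**What to change.** In Sections 1.1 and 3, make the Active-versus-Sham difference in PSQI change from Day 0 to Day 30 the primary efficacy outcome. Restate each Section 3 secondary outcome (PSQI-A and NW Likert, PCL-5 and PHQ-9, FOSQ-10 and VR-12, TRNS, ISI) as Active versus Sham at Day 30. Label within-arm changes descriptive.

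If the sponsor prefers to keep the Active-only change as a primary outcome, add a sentence saying that efficacy success also requires the Active-versus-Sham test in Section 7.2 to succeed.

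The cost is wording. No further participants, visits or data are needed, because 60 completers per arm already power the contrast. The one small loss is a stand-alone efficacy claim from the Active arm.

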## 1.2. Schematic

### 1.3. Schedule of Activities

Study Activities Table:

Study Activity	Pre-Tx	Visit 1	Calibration	Start Up Call	Help Calls	Check Up Call 1	Assessment Call	Check Up Call 2	Visit 2	Visit 3	Visit 4
Study Day	Before Day 0	Day 0	Days 0-3	Day 1	Days 2-6 (Optional)	Day 7	Day 14 (+/-3)	Day 21 (+/- 2)	Day 30 (+/- 7)	Day 60 (+/- 7)	Day 90 (+/- 7)
Recruitment	X										
Chart Review	X										
Phone Screen	X										
Inclusion/Exclusion	X	X									
ICF and HIPAA		X									
Modified Dysken I		X a									
AUDIT		X b									
DAST-10		X c									
Demographics		X									
Medical History		X									
Blood Pressure		X							X		
Med Reconciliation		X							X	X	X
PSQI		X					X		X	X	X
PSQI-A		X							X		
ESS		X							X	X	X
ISI		X							X	X	X
PCL-5		X					X		X	X	X
CAPS-5		X									
VR-12 (QOL)		X							X	X	X
TRNS		X							X	X	X

FOSQ-10		X							X		
PHQ-9		X					X		X	X	X
C-SSRS Lifetime		X							X	X	X
Blinding Assessment Questionnaire									X		
NW Likert Scale		X							X	X	X
Daily Use Questionnaire (Days 1-90)				X	X	X	X	X	X	X	X
Calculate Cutoffs/Eligible ?		X									
Dispense NW Devices		X									
Train Subject		X									
Activate Devices		X									
C-SSRS Since Last Contact									X	X	X
Payment of Subject(Bi weekly)	See Reimbursement Section 6.15										
Start Up Call				X							
Calibration			X								
Active/Sham Treatment			Post- Calib. f								
Help Calls Questionnaire (Optional)					X	X		X			
Checkup Phone Call						X		X			
Sham Cross- over to Active Treatment									X		

a—Administered DURING informed consent process to ensure subjects are capable of consent. Subjects must get all responses correct to be enrolled into the study, b-Exclude if score is equal to or greater than 8. c-Exclude if score is greater than 2. f-Only the Active System goes through calibration and on to Active Treatment.

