**6.4. Enrollment: Visit 1, Day 0**

Those who pass the telephone pre-screening will be scheduled for an Enrollment Visit (Visit 1, Day 0).

Procedures to be done at this visit include:

1. Re-check of inclusion/exclusion criteria prior to signing enrollment forms.
2. Signing of Informed Consent Form (ICF) and HIPAA
3. Completion of a Demographics Form
4. Baseline Psychometric Instruments:
  - a. Pittsburgh Sleep Quality Index (PSQI)
  - b. PSQI Addendum for PTSD (PSQI-A)
  - c. PCL-5 Checklist (past 1 month)
  - d. Clinician-Administered PTSD Scale for DSM-5 (CAPS-5)
  - e. Patient Health Questionnaire-9 past 1-month version (PHQ-9) (Score greater than or equal to 20 indicates severity of depression too great for this study. Score of 1 or more on the suicide ideation item [question #9] to trigger a risk assessment by PI and a licensed Behavioral Health Provider.)
  - f. Epworth Sleepiness Scale ESS: On question #8 any score above “0” will prompt an additional question:
    1. Do you drive (“get behind the wheel”) when you are drowsy?
      - a. Answer must be “No” to be enrolled in the study due to safety concerns.
  - g. DAST-10: Exclude if score is greater than two (2).
  - h. AUDIT: Exclude if score is equal to, or greater than, eight (8).
  - i. Functional Outcomes of Sleep Questionnaire (FOSQ)
  - j. Insomnia Severity index (ISI)
  - k. Trauma Related Nightmare Scale (TRNS)

- l. VR-12 Quality of Life (VR-12)
- m. NW Likert Scale for Sleep Quality (NW Likert) 7-day
- n. Columbia-Suicidality Severity Rating Scale, Lifetime and Recent version (C-SSRS) (responses in the High-Risk range will make the subject ineligible).
  - i. After further assessment with the PI, Study Staff will contact the healthcare provider that has been trained to perform a suicide assessment for all subjects with a rating greater than “LOW”.
- o. RedCAP collection questionnaire: What type or types of traumas led to your PTSD? (Choose the primary type of trauma that applies) 1) Combat/blast trauma 2) Sexual Trauma/Rape/Sexual Assault 3) Natural Disaster 4) Childhood physical abuse 5) Accident, such as a car accident 6) Other (a secondary choice would appear for free text).
5. Baseline health assessments

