### **2. Psychometric Instruments:**

- a. Pittsburgh Sleep Quality Index (PSQI)
- b. PSQI Addendum for PTSD (PSQI-A)
- c. PCL-5
- d. Insomnia Severity Index (ISI)
- e. (PHQ-9) (Score of 1 or more on the suicide ideation item [question #9] to trigger a risk assessment by a licensed Behavioral Health Provider if deemed necessary by the PI.)
- f. Epworth Sleepiness Scale ESS
- g. Functional Outcomes of Sleep Questionnaire (FOSQ)
- h. Trauma Related Nightmare Scale (TRNS)
- i. VR-12 Quality of Life (VR-12)
- j. NW Likert Scale for Sleep Quality (NW Likert)
- k. Columbia-Suicidality Severity Rating Scale, Since Last Contact version (C-SSRS)
  - i. If deemed necessary by the PI, Study Staff will contact a healthcare provider that has been trained to perform a suicide assessment if there is any risk of suicide.
- l. Blinding Assessment Questionnaire

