#### **7.5. Primary Safety Analyses**

The hypothesis for the primary safety endpoint is that the Active NW System will not lead to worsening of daytime sleepiness as measured by the Epworth Sleepiness Scale, which provides a score between 0 and 24 with higher values indicating a higher degree of sleepiness. Specifically, the hypothesis is that on-average a user of NW will have a mean ESS score measured at 30 days following the start of NW digital therapeutic system use that is not higher than their ESS score measured at baseline. This hypothesis will be tested similarly to the primary efficacy hypothesis using a one sample t-test.

The hypothesis for the secondary safety endpoint is that the Active NW System will not lead to an increase in suicide risk as assessed by Columbia-Suicide Severity Rating Scale (C-SSRS) from baseline (Day 0) to Day 30. C-SSRS has ratings of "none", "low", "moderate", and "high". Those possible participants rated as "high" on the C-SSRS at Visit 1 will NOT qualify for the study and, if deemed necessary by the PI, will be given immediate assessment by a licensed Mental Health Provider, who will determine the next therapeutic steps. This hypothesis will be tested similarly to the primary efficacy hypothesis using a one sample t-test.

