#### **9.1.3. Assessment of Potential Risks and Benefits**

Study inclusion and exclusion criteria were designed to only include subjects already suffering from sleep disorder and therefore most likely to benefit from the intervention.

Since the intervention is delivered through a non-invasive smartwatch, study participants may simply discontinue wearing the watch if the intervention is contributing to deteriorating sleep quality.

The trial includes a primary safety endpoint designed to evaluate worsening sleep quality:

1. Epworth Sleepiness Scale

The trial also includes a secondary safety endpoint designed to evaluate worsening suicidal risk:

1. Columbia-Suicide Severity Rating Scale (C-SSRS LT) will be administered at the beginning and end of the study.
  - a. The Lifetime and Recent version will be used to determine if the subject is suitable for this study.
    - i. Potential Subjects that have a rating of “High” will be excluded from this study.

- ii. Since a “High” rating is an imminent safety risk, study staff will immediately call/page the PI, and if needed, a licensed staff member to conduct a safety assessment.
  1. If there isn’t a licensed staff person available, the subject will be TAKEN to the Hospital Emergency Room.
- b. At the 30, 60, and 90 day visits(+7 days), the subject will take another C-SSRS, the Since Last Contact version.
  - i. Either an increase in or a “High” score is an imminent safety risk, so study staff will immediately call/page licensed staff member to conduct a safety assessment.
    1. If there isn’t a licensed staff person available, the subject will be TAKEN to the Hospital Emergency Room.

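### The C-SSRS safety endpoint does not say which baseline recall window is scored and rests on an Active-only mean, so worsening of suicide risk can be understated or missed

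*Protocol*

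**What the plan says.** **Endpoint.** Protocol Section 3 gives the outcome as "Difference between the average Columbia-Suicide Severity Rating Scale (C-SSRS) at baseline" against Day 30, and names the two forms: "baseline (Day 0-Lifetime and Recent version) and C-SSRS at Day 30 (Since Previous Contact version". The visit procedures agree. Section 6.4 has "Columbia-Suicidality Severity Rating Scale, Lifetime and Recent version (C-SSRS" at Visit 1, and Section 6.12 has "Columbia-Suicidality Severity Rating Scale, Since Last Contact version (C-SSRS" at Day 30. Sections 6.13 and 6.14 list the same follow-up form, and Section 9.1.3 says that at Days 30, 60 and 90 "the subject will take another C-SSRS, the Since Last Contact version".

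**Arm.** The Synopsis (Section 1.1) words the outcome as "No increase in C-SSRS severity score between Day 0 and Day 30 in the Active System".

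**Test.** Section 7.5, repeated in the SAP, describes four ratings (none, low, moderate, high) and states: "This hypothesis will be tested similarly to the primary efficacy hypothesis using a one sample t-test". Participants rated high at Visit 1 are not eligible (Sections 5.2, 7.5 and 9.1.3).

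**Not stated anywhere:** which part of the Day 0 form is scored, how the ratings become numbers, the recall period of the Recent part, and any margin for the claim of no increase.

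**Inconsistencies.** The Schedule of Activities (Section 1.3) ticks a row named "C-SSRS Lifetime" at Day 0 and again at Days 30, 60 and 90, next to a separate row for the follow-up form. The endpoint is listed under primary safety in Sections 1.1 and 3, but is called secondary in Sections 7.5 and 9.1.3 and in the SAP.

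**The concern.** A change score needs both ends measured over comparable periods. On a common scoring rule, a lifetime rating is at least as high as a recent rating taken on the same day. Choosing the lifetime part therefore lowers the change score for every participant with older ideation that has since resolved. An analyst following the plan could make either choice, and the sign of the result could depend on it.

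Two further weaknesses remain even if the windows match. A mean of four ordered levels lets small improvements in several people cancel a severe worsening in a few. And a one-sample test against zero with no margin cannot support the stated objective of showing that suicide risk does not rise, because a non-significant result is only a failure to detect.

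At stake is a headline safety objective in people with PTSD symptoms. Day 30 is also the last assessment before sham participants cross over (Section 1.3), so it is the only point with a randomised comparison.

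**Working it through.** The documents give no sample size, SD, margin or expected rate for C-SSRS, so there is no figure to reproduce. From the documents come the four levels (scored here 0 to 3), the exclusion of high at entry, the one-sample t-test, and 60 completers per arm (Section 7.3). The rating distributions are assumptions.

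**1. Effect of the baseline window.**

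Assume recent baseline ratings of 80% none, 15% low and 5% moderate. Assume 10% of participants worsen by one level by Day 30 and the rest are unchanged. A share *s* also carries an older lifetime rating, half low and half moderate. The lifetime rating is the higher of the recent and older ratings.

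- Recent baseline: mean change = 0.10 × 1 = +0.10.
- Average excess of lifetime over recent among those with an older rating: 0.80 × 1.5 (recent none, older rating averages 1.5) + 0.15 × 0.5 × 1 (recent low, older moderate) + 0.05 × 0 = 1.275.
- Lifetime baseline: mean change = 0.10 - 1.275*s*.

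| Share *s* | Mean change, lifetime baseline | Significant worsening | Significant improvement |
|---|---|---|---|
| 0% | +0.10 | 86% | 0% |
| 10% | -0.03 | 2% | 4% |
| 20% | -0.16 | 0% | 42% |
| 30% | -0.28 | 0% | 85% |
| 50% | -0.54 | 0% | about 100% |

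The last two columns come from a simulation of 4,000 trials per row with 60 Active completers and a two-sided 5% test. Its mean changes match the formula. With a recent baseline, worsening was significant in about 86% of runs whatever *s* was. The sign flips at *s* = 0.10/1.275, about 8%. The simulation has no random month-to-month fluctuation, so 86% is favourable to the test.

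Sensitivity: if moderate were also barred at entry, the 80% and 15% rescale to 84.2% and 15.8%, and an older rating can only be low. The formula becomes 0.10 - 0.842*s*, giving -0.15 at 30% and -0.32 at 50%. The bias is smaller but in the same direction.

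**2. A single worked case.**

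Take 60 completers with no recent ideation at baseline, of whom 18 have a lifetime rating of moderate. During the trial 12 go from none to moderate (4 of the 18 and 8 of the other 42).

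- Recent baseline: 12 × 2/60 = +0.40, p = 0.0003.
- Lifetime baseline: (12 × 2 - 18 × 2)/60 = -0.20, p = 0.20.

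**3. The mean with matched windows.**

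- Three of 60 go from none to high and nobody else changes. Mean = 3 × 3/60 = 0.15. Variance = (27 - 60 × 0.15²)/59 = 0.435, so SD = 0.659. Then *t* = 0.15/(0.659/√60) = 1.76, two-sided p = 0.08. This is not flagged under the two-sided 0.05 rule that Section 7.2 sets for efficacy.
- Two go from none to high while six go from low to none: (2 × 3 - 6 × 1)/60 = 0 exactly.

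**The case against.** **The recent part may be what is meant.** The Day 0 form has a recent part. Section 9.1.3 treats a high baseline rating as an imminent risk, and Section 5.2 refers to ideation within the last month. Both suggest a rating of current risk. If only that part is scored, the window bias largely disappears. This stands, and so the defect is an unspecified scoring rule, not a stated choice of lifetime scoring. The labels in Sections 1.3 and 14 lean the other way, and the SAP does not settle it.

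**Success is not automatic.** A reader might infer that the lifetime window pushes the change down whatever the device does, so that the objective is met almost by construction. The documents do not support that. Lifetime scoring is nowhere stated, the bias is nil if nobody has an older rating, and because high is excluded at entry a Day 30 rating can exceed even a lifetime baseline.

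**The sham arm is not wholly ignored.** Protocol Section 7.6 and the SAP plan repeated-measures comparisons between groups for all survey types and chi-square or Fisher tests for categorical variables, and the SAP analyses all measures by assigned group. So a between-arm look at C-SSRS is generically foreseen. It is not the test named for this endpoint, and no worsening outcome is defined for it.

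**Individuals are protected.** Section 9.1.3 requires immediate assessment for any increase or a high score, and PHQ-9 item 9 triggers review at the same visits. It would be wrong to say that worsening goes unseen clinically. But this does not repair the endpoint, and the increase trigger does not name its baseline rating either.

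**A two-arm comparison is not powerful either.** Three of 60 against none of 60 gives Fisher p = 0.24, and power for 5% against 15% at 60 per arm is about 45%. This stands. The gain is an honest estimate with its uncertainty and visible cases, not a sharper test.

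**Conclusion.** The concern holds as a gap in specification together with a poorly matched test. The endpoint names forms with different recall periods without saying which baseline part counts. If the lifetime part is used, the change is biased downward relative to a recent baseline. Under the assumptions above, a true +0.10 becomes -0.03 to -0.54 as the share with older ratings runs from 10% to 50%, with no bias at 0%. That share is unknown, so the documents fix neither the size nor, in every case, the net direction of the observed change.

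Independently of the window, an Active-only mean with no margin can miss three participants in 60 moving from none to high, and non-significance would not show the absence of an increase. The inconsistent schedule row and the primary or secondary label are lesser matters, but should be settled in the same edit.

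**What to change.** In Protocol Sections 3 and 7.5 and in the SAP:

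1. Score baseline from the Recent part of the Day 0 form and state its recall period. State the period covered at Day 30 too, since a Day 21 call precedes that visit and could be read as the last contact.
2. Replace the one-sample t-test with the number and percent in each randomised arm whose rating rose from Day 0 to Day 30: any increase, and increase to moderate or high. Give the Active-Sham risk difference with an exact 95% CI, and show how many in each arm lack a Day 30 rating.
3. List every participant whose rating increased, by arm, with both ratings.
4. Reconcile the Lifetime row in the Section 1.3 schedule with Sections 6.12 to 6.14 and 9.1.3.
5. Give the endpoint one status, primary or secondary, throughout.

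The cost is wording. The Day 0 form already includes a recent part and both arms are assessed at Day 0 and Day 30, so no new data are needed.
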